8. STUDY DESIGN

8.1. Overall Study Design

This is a multicenter Phase II study of an intratumoral injection of Ad-RTS-hIL-12 (████████) and veledimex (20 mg) administered PO in combination with cemiplimab-rwlc (350 mg) administered intravenously (IV) in subjects with recurrent or progressive glioblastoma. This study will determine the safety and efficacy of Ad-RTS-hIL-12 + veledimex when administered in combination with cemiplimab-rwlc, based on the safety profile observed and overall survival, respectively.

This study includes a Screening Period, Treatment Period, and Survival Follow-up. After the informed consent form (ICF) is signed, subjects will enter the Screening Period to be assessed for eligibility ██████████

Subjects will receive cemiplimab-rwlc on Day -7 (± 3 days). On Day 0 (day of Ad-RTS-hIL-12 administration) subjects will take one dose of veledimex 3 ± 2 hours prior to injection and Ad-RTS-hIL-12 ██████████ will be administered by freehand injection. Ad-RTS-hIL-12 will be delivered intratumorally or at the margin of the tumor for a total volume of 0.1 mL following resection (subtotal or gross total). The total amount delivered to each site will be recorded in the eCRF. If the total administered volume is less than planned, the reason will be provided. Care should be taken to avoid intraventricular or basal cisternal injection or other critical locations.

After the Ad-RTS-hIL-12 injection, veledimex will be administered orally for 14 days. The first post craniotomy veledimex dose is to be given on Day 1. Subsequent veledimex doses are to be taken once daily, in the morning. Dosing on Days 2-14 should be at approximately the same time of day (+/- 1 hours) as the Day 1 dosing.

Subjects will receive a dose of cemiplimab-rwlc (350 mg) IV on Day 15 and every three weeks thereafter (Q3W) until documented progression by immunotherapy Response Assessment for Neuro Oncology (iRANO) criteria, unacceptable toxicity, subject withdrawal or completing the follow-up period. Delays in cemiplimab-rwlc dosing due to toxicities are allowed at the discretion of the Principal Investigator in consultation with the Medical Monitor, for up to 14 days.

A formal Safety Review Committee (SRC) will be comprised of the study Investigators and the Medical Monitor.

After the first six patients have been enrolled and administered Ad-RTS-hIL-12 and veledimex in combination with at least one post Ad-RTS-hIL-12 dose of cemiplimab-rwlc, enrollment will be paused to allow for additional safety follow-up and assessment. The SRC will review safety data after the 6th subject has reached Day 28 and decide if enrollment should occur at the same dose and schedule of the investigational products.

8.2. Study Oversight for Safety Evaluation

Safety oversight will occur through the site investigator and medical monitor. A formal SRC, guided by the SRC charter, will include the study investigators, the medical monitor and other appropriate sponsor representatives and will provide overall safety oversight. Additional

external medical and scientific experts may also be invited to participate in the reviews as needed and appropriate and as decided by the SRC. If a significant safety event occurs, the SRC will convene to evaluate the safety event(s) and make a recommendation and decision on the enrollment and continued treatment of subjects.

9. SUBJECT SELECTION

Subjects with supratentorial glioblastoma who have not previously been treated with inhibitors of immuno-checkpoint pathways (e.g., anti-PD-1, anti-PD-L1, anti-PD-L2, anti-CD137, or anti-CTLA-4 antibody) or other agents specifically targeting T cells.

9.1. Inclusion Criteria

1. Male or female subject ≥ 18 and ≤ 75 years of age
2. Provision of written informed consent for tumor resection (subtotal allowed), tumor biopsy, samples collection, and treatment with investigational products prior to undergoing any study-specific procedures
3. Histologically confirmed glioblastoma from archival tissue
4. Evidence of tumor recurrence/progression by magnetic resonance imaging (MRI) according to Response Assessment in Neuro-Oncology (RANO) criteria after standard initial therapy. Multifocal disease is allowed, but subjects must not have more than 5 enhancing lesions.
5. Previous standard-of-care antitumor treatment including surgery and/or biopsy and chemoradiation. At the time of registration, subjects must have recovered from the toxic effects of previous treatments as determined by the treating physician. The washout periods from prior therapies are intended as follows: (windows other than what is listed below should be allowed only after consultation with the Medical Monitor)
 - a. Nitrosoureas: 6 weeks
 - b. Other cytotoxic agents: 4 weeks
 - c. Antiangiogenic agents: 4 weeks
 - d. Targeted agents, including small molecule tyrosine kinase inhibitors: 2 weeks
 - e. Vaccine-based or CAR-T therapy: 3 months
6. Able to undergo standard MRI scans with contrast agent before enrollment and after treatment
7. Karnofsky Performance Status ≥ 70
8. Adequate bone marrow reserves and liver and kidney function, as assessed by the following laboratory requirements:
 - a. Hemoglobin ≥ 9 g/L
 - b. Lymphocytes $>500/\text{mm}^3$
 - c. Absolute neutrophil count $\geq 1500/\text{mm}^3$
 - d. Platelets $\geq 100,000/\text{mm}^3$
 - e. Serum creatinine $\leq 1.5 \times$ upper limit of normal (ULN)
 - f. Aspartate transaminase (AST) and alanine transaminase (ALT) $\leq 2.5 \times$ ULN.
 - g. Total bilirubin $<1.5 \times$ ULN

- h. International normalized ratio (INR) and activated partial thromboplastin time (aPTT) or partial thromboplastin time (PTT) within normal institutional limits
9. Female of child bearing potential* and sexually active male subjects must agree to practice highly effective contraception prior to the start of the first treatment, during the study, and for at least 4 months after the last dose. Highly effective contraceptive measures include stable use of combined (estrogen and progestogen containing) hormonal contraception (oral, intravaginal, transdermal) or progestogen-only hormonal contraception (oral, injectable, implantable) associated with inhibition of ovulation initiated 2 or more menstrual cycles prior to screening; intrauterine device (IUD); intrauterine hormone-releasing system (IUS); bilateral tubal ligation; vasectomized partner; and or sexual abstinence**.

* Postmenopausal women must be amenorrheic for at least 12 months in order not to be considered of childbearing potential. Pregnancy testing and contraception are not required for women with documented hysterectomy or tubal ligation.

** Sexual abstinence is considered a highly effective method only if defined as refraining from heterosexual intercourse during the entire period of risk associated with the study treatments. The reliability of sexual abstinence needs to be evaluated in relation to the duration of the clinical trial and the preferred and usual lifestyle of the patient.

10. Normal cardiac and pulmonary function as evidenced by a normal ECG with QTc \leq 450 msec and peripheral oxygen saturation (SpO2) \geq 92% on Room air by pulse oximetry

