Veledimex dose and diary ^v			X ^{s, t}	X ^{s, t}	X	X ^u	X	X	X
MRI scans ^z	X ^z			X ^{z, aa}					

Table 1: Schedule of Study Procedures (continued)

Activity	Treatment							Long Term Follow-up
	Day 14	Day 15	Day 22	Day 28	Day 36 ±3 days	Day 57 ±3 days	Every 3 weeks ^b ±7days	
Informed consent								
Medical/Cancer history ^d								
Physical exam ^e , including targeted neurological exam	X				X		X	
Karnofsky PS ^f	X				X		X	
Height (screen) and weight	X				X			
Vital signs ^g	X				X		X	
Adverse events ^h					CONTINUOUS			
Concomitant medications ^h					CONTINUOUS			
Survival status ⁱ					CONTINUOUS			
Pregnancy test ^j				X	X		X	
Hematology ^k	X		X		X	X	X	
Coagulation ^l	X				X			
Serum chemistry ^m	X		X		X	X	X	
Urinalysis ⁿ	X		X			X	X	
Thyroid panel ^o	X				X	X	X	
ECG ^p	X				X		X	
Confirm eligibility								
Cemiplimab-rwlc dose ^q		X			X	X	X	
Ad-RTS-hIL-12								
Veledimex dose and diary	X ^v							
	[REDACTED]	[REDACTED]			[REDACTED]			
	[REDACTED]	[REDACTED]			[REDACTED]			
	[REDACTED]	[REDACTED]			[REDACTED]			
MRI scans ^z						X ^z		X ^z
	[REDACTED]	[REDACTED]			[REDACTED]			
	[REDACTED]	[REDACTED]			[REDACTED]			

^h Screening assessments must be conducted within 30 days prior to dosing with Ad-RTS-hIL-12 + veledimex.

^{**} Day -7 dosing with cemiplimab-rwlc may be performed within ± 3 days.

^a The PI will review all results of laboratory tests drawn within 24 hours prior to surgery.

^b Every 3 weeks from Day 57

^c Every 8 weeks from Day 57 in addition to assessments performed every 3 weeks

^d Medical history includes demographic information, relevant medical and surgical history. Cancer history includes current cancer diagnosis, prior treatment (regimen[s], doses, start and stop dates, and

any associated residual toxicity), and best response for each regimen.

^e A complete physical examination including a neurological exam and mental status is required at baseline and discharge from hospital. Targeted neurological exams thereafter

KPS is required at Screening, Day -7, Day 0, Day 14, Day 36 and every 3 weeks thereafter.

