⁵ Blood pressure, pulse, temperature, and respiration will be recorded. Pulse oximetry peripheral oxygen saturation (SpO₂) will be recorded at Screening, Day -7, Day 0, Day 3, Day 7, Day 14, Day 36 and every 3 weeks from Day 57. Blood pressure should be monitored closely, with hydration as needed to prevent hypotension after veledimex administration. Subjects must be instructed to maintain adequate oral hydration on and between veledimex dosing days; sites must closely monitor hydration status.

^h Concomitant medications will be monitored and recorded throughout the study. Medications received in the period preceding consent (~28 days), in addition to those ongoing at screening, will be captured in the eCRF. Non-serious events from ICF signature until administration of first study drug that are not study related will be reported as medical history. Concomitant medications and AEs/SAEs must be recorded in the eCRF through 90 days after the last dose of any study drug. Ongoing drug-related AEs should be followed until resolution unless none is expected. New anti-cancer medications should be captured through completion of survival follow-up.

ⁱ Subjects will be followed to document start of new anticancer therapies and survival status for 2 years following administration of Ad-RTS-hIL-12.

^j Serum pregnancy test at Screening for females of childbearing potential, must be within 72 hours prior to first dose of cemiplimab-rwlc; urine or serum pregnancy test on all other days.

^k Hematology: Complete blood count, white blood count with differential, red blood cell count, red blood cell indices, hematocrit, hemoglobin, and platelet count. The Day 0 testing should be obtained prior to veledimex dosing.

¹ Coagulation: aPTT, INR, erythrocyte sedimentation rate and C-reactive protein. The Day 0 testing should be obtained prior to veledimex dosing.

¹⁰ Serum Chemistry: AST, ALT, lactate dehydrogenase, alkaline phosphatase, lipase, amylase, creatinine, total bilirubin, total protein, albumin, blood urea nitrogen, glucose, sodium, potassium, chloride, calcium, phosphorus, and bicarbonate. The Day 0 testing should be obtained prior to veledimex dosing.

^a Urinalysis Panel (dipstick): appearance, pH, specific gravity, glucose, protein/albumin, blood, ketones, bilirubin, nitrates, and leukocyte esterase. In addition, a microscopic exam for casts, crystals and cells may be done if indicated. The Day 0 testing should be obtained prior to veledimex dosing.

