Thyroid Panel: free triiodothyronine (FT3), free thyroxine (FT4), and thyroid-stimulating hormone (TSH).

^P Standard 12-lead ECG single measurement at each time point. The Day 0 testing should be obtained prior to veledimex dosing.

⁹ Eligibility must be confirmed within 24 hours prior to dosing with cemiplimab-rwlc. In the event of toxicities likely related to cemiplimab-rwlc, the PI and the Medical Monitor will individualize the management of cemiplimab-rwlc dosing in general accordance with the Investigator's Brochure. Doses must be at least 21 days apart. Delays of up to 14 days are acceptable for toxicity, in consultation with the medical monitor.

¹ Ad-RTS-hIL-12 intratumoral injection should be administered by freehand injection. Subjects must be instructed to maintain adequate oral hydration during the Treatment Period; sites must closely monitor subjects' hydration status. Because of the potential for toxicity (e.g., fevers, chills, fatigue, and dehydration), administration of prophylactic antipyretics is recommended after injection of Ad-RTS-hIL-12.

⁵ Each subject will be carefully monitored for any local reactions and/or hypersensitivity reactions following the Ad-RTS-hIL-12 injection and velevidex administration. Subjects should be instructed to call the clinical site if headache, hemiparesis, seizure, or other local reactions develop anytime and especially between study visits.

[†] The first post-resection veledimex dose will be given on the next day, designated as Day 1, under supervision of the clinical staff to ensure there are no difficulties swallowing the capsule. Subsequent veledimex doses are to be taken once daily, in the morning and within 30 minutes of a regular meal.

^u The Day 3 dose should be held until Day 3 labs have been reviewed. Subjects should not be dosed unless lymphocyte counts, platelet counts, and liver function tests have changed by $\leq 20\%$ from baseline values and the Grade of any abnormality has not increased. Medical monitor consultation is then advised.

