12. Prior exposure to inhibitors of immuno-checkpoint pathways (e.g., anti-PD-1, anti-PD-L1, anti-PD-L2, anti-CD137, or anti-CTLA-4 antibody) or other agents specifically targeting T cells.
13. Use of medications that induce, inhibit, or are substrates of CYP450 3A4 prior to veledimex dosing without consultation with the Medical Monitor
14. Presence of any contraindication for a neurosurgical procedure
15. Use of heparin or other anti-coagulation therapy, or acetylsalicylic acid (ASA), or anti-platelet drug within Day -7 to Day 21 should not be used unless necessary to treat a life-threatening illness. Prophylactic subcutaneous heparin per institutional protocol for prevention of DVT may be allowed based on discussion with the Medical Monitor. Concomitant medications should continue to be reviewed in consultation with the Medical Monitor.
16. Unstable or clinically significant medical condition that would, in the opinion of the Investigator or Medical Monitor, jeopardize the safety of a subject and/or their compliance with the protocol. Examples include, but are not limited to, history of myocarditis or congestive heart failure (as defined by New York Heart Association Functional Class III or IV), unstable angina, serious uncontrolled cardiac arrhythmia, myocardial infarction within 6 months of screening, active interstitial lung disease (ILD)/pneumonitis or a history of ILD/pneumonitis requiring treatment with systemic steroids uncontrolled asthma, or colitis.

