3.6. Inclusion and Exclusion Criteria

The details of Inclusion and Exclusion criteria are listed in Section 9.1 and 9.2 of the protocol. All inclusion/exclusion information on safety patients will be included in a by-patient listing. For patients who did not satisfy these criteria, the criteria numbers will be listed with the deviation. The key change to the inclusion criteria depicted in amendment 2 was that multifocal disease was not prohibited; although, subjects must not have more than 5 enhancing lesions.

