4.4. Data Management

Ziopharm Data Management directs and oversees the administration of the ATI001-204 eCRF database. The clinical trial data from all screened and enrolled subjects populate the ATI001-204 database which is also managed by a third-party contract research organization (CRO). In addition, the ATI001-204 protocol provided for study objectives for which the data obtained are not part of the eCRF. Instead, the data are acquired based on the data transfer agreements (DTA) from 7 external data sources denoted as “vendors” summarized in [Table 1](#) below. Specifically:

- The ATI001-204 clinical database consists of N=40 FAS subjects for whom at least one of the following study treatments were received: Ad-RTS-hIL-12, veledimex, cemiplimab.
- The imaging data objective originally to be undertaken with Bioclinica was put on hold and not performed.

- For completeness it is noted that there are subjects who also have data in the database who are classified as screen failures for whom we are not counting for the purpose of this description. Subjects that were enrolled but did not receive treatment were withdrawn and will not be included in any analysis population.
- A summary of the number of screen failures signing an informed consent is provided in the subject disposition.
- Extraction of Raw SAS datasets from the EDC database will be converted into Study Data Tabulation Model (SDTM) SAS datasets based on CDISC.

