4.7.2. Protocol Deviations

A protocol deviation is any change, divergence, or departure from the study design or procedures defined in the protocol. Important protocol deviations are a subset of protocol deviations that may significantly impact the completeness, accuracy, and/or reliability of the study data or that may significantly affect a subject's rights, safety, or well-being. In general, no subject was planned to be removed from any analysis population because of a protocol deviation.

In accordance with ICH E3, patient eligibility violations and important post- treatment protocol deviations will be identified and listed by patient and study center. Major deviations that are considered to potentially impact the efficacy or safety analyses will be tabulated. Important protocol deviations will be identified prior to database lock. Protocol deviations will be listed and summarized by type.

- Deviation from inclusion/exclusion criteria.
- Withdrawal criteria met during the study, but subject was not withdrawn.
- Prohibited concomitant medications.
- Treatment deviation.
- Other protocol deviation.

All protocol deviations will be categorized as either major or minor. The list of protocol deviations along with whether the deviation is classified denoting a major or minor categorization will be finalized prior to database lock.

Major protocol deviations will be presented in a summary table by protocol deviation category for the FAS. Protocol deviations will be presented in a listing.

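### Inclusion criterion 8a sets haemoglobin at 9 g/L (0.9 g/dL), which screens out no plausible candidate; the unit is almost certainly meant to be g/dL and should be corrected (minor)

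*Protocol*

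**What the plan says.** Inclusion criterion 8 in Protocol Section 9.1 uses a list of laboratory limits to judge marrow, liver and kidney function. The first, 8a, reads "Hemoglobin ≥ 9 g/L". The synopsis has the same line. So do the synopsis and Section 9.1 of both superseded protocol versions in the same document, so a text-extraction fault is unlikely.

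The other places that bear on haemoglobin at or near entry give no number:

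- Table 1, footnote k, defines the panel drawn at Screening, Day -7 and Day 0: "Hematology: Complete blood count, white blood count with differential, red blood cell count, red blood cell indices, hematocrit, hemoglobin, and platelet count".
- Table 1, footnote q: "Eligibility must be confirmed within 24 hours prior to dosing with cemiplimab-rwlc".
- Table 1, footnote a: "The PI will review all results of laboratory tests drawn within 24 hours prior to surgery".
- Exclusion 14: "Presence of any contraindication for a neurosurgical procedure". Inclusion 5 (recovery from earlier treatment toxicity) and exclusion 16 (unstable or significant medical conditions) are likewise left to clinical opinion.

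SAP Section 3.6 refers back to the protocol for eligibility and plans a by-patient listing: "For patients who did not satisfy these criteria, the criteria numbers will be listed with the deviation".

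**The concern.** 8a is a working entry limit before craniotomy, vector injection and PD-1 blockade, in patients whose permitted earlier treatment includes nitrosoureas and other cytotoxic drugs. The neighbouring lymphocyte, neutrophil and platelet limits are real thresholds. The haemoglobin limit, read literally, is not.

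Two things follow from the literal text. Keeping out a clearly anaemic candidate depends on physician judgement, because the stated number cannot do it. And a subject at 7 or 8 g/dL satisfies 8a as written, so the listing of unmet criteria would not show that subject against 8a. A reader could then take an empty 8a entry to mean that nobody entered below 9 g/dL, which the listing cannot establish.

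**Working it through.** **Inputs.** The written limit is 9 g/L (Protocol synopsis and Section 9.1, criterion 8a). The Karnofsky minimum is 70 (criterion 7). The intended limit of 9 g/dL is an assumption; the documents do not state it. No calculation in the plan produces the haemoglobin limit, so there is no derived figure to reproduce.

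**Step 1: convert the written limit.** 1 dL is 0.1 L, so g/dL = (g/L) ÷ 10, and 9 ÷ 10 = 0.9 g/dL.

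**Step 2: convert the assumed limit.** 9 g/dL × 10 = 90 g/L. The ratio of assumed to written limit is 90 ÷ 9 = 10.

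**Step 3: find the values treated differently.** These run from 0.9 up to, but not including, 9.0 g/dL. For example:

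| Haemoglobin | In g/L | 8a as written (9 g/L) | 8a if 90 g/L was meant |
|---|---|---|---|
| 7.0 g/dL | 70 | passes | fails |
| 8.0 g/dL | 80 | passes | fails |
| 9.0 g/dL | 90 | passes | passes |

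That no candidate would fail 0.9 g/dL is basic physiology, not a figure in the documents.

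**Step 4: look for a limit elsewhere.**

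- The laboratory panels in Table 1 and Protocol Section 12.3, and SAP Section 9.2.1, name haemoglobin without a limit.
- The stopping rules (Protocol 10.9) and the veledimex dose rules (Protocol 10.10, Table 2) apply after entry. Their haematologic triggers are toxicity grades or a platelet count.
- The eligibility check before cemiplimab is made against the criteria as written, so it inherits the error in 8a.
- Day 0 haemoglobin belongs to the pre-surgery review and comes after the eligibility confirmation.

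None of these supplies a numerical floor.

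**Step 5: trace the effect on the statistics.** The sample size, the safety-rate interval, the toxicity boundary and the Kaplan-Meier analysis of OS do not use haemoglobin. Correcting the unit changes none of them.

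**Step 6: count the subjects affected.** SAP Section 4.4 gives the treated set: "The ATI001-204 clinical database consists of N=40 FAS subjects for whom at least one of the following study treatments were received". No haemoglobin values are reported, so the number below 9 g/dL cannot be derived and may be zero.

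**The case against.** The strongest reply is that this is an obvious slip. A limit that no living candidate could fail would not be taken for a real threshold, so sites would naturally read 9 g/dL. For harm to occur, an investigator would have to apply 0.9 g/dL literally, and the subject would then have to pass inclusion 5, exclusions 14 and 16, and the investigator's review of laboratory results before surgery. The trial is also past the stage where an entry criterion protects anyone: the SAP describes 40 treated subjects, prepares for database lock and supports an abbreviated report. All of this stands, and it holds the point at minor. It does not make the written limit right, and it does not supply the number from elsewhere.

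A reader might infer that a low entry haemoglobin would go unseen. The documents do not support that. SAP Section 9.2 classifies laboratory results against normal ranges and plans shift tables. The table lists in the SAP appendices include abnormal and clinically significant values (Tables 14.3.4.1 and 14.3.4.2) and hematology summaries (Tables 14.3.6.3 and 14.3.6.4). Section 10.6 drops vital signs, examinations and ECG, but not laboratory data. What is lost is only the flag against 8a.

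A reader might also infer that subjects below 9 g/dL must be barred from, or forced into, deviation status, with a knock-on effect on the per-protocol set and primary OS. That does not follow either. SAP Section 4.7.2 says "A protocol deviation is any change, divergence, or departure from the study design or procedures defined in the protocol", which on the literal text favours treating them as compliant. If sites and sponsor worked to 9 g/dL, recording a deviation would also be reasonable. The same section leaves the major or minor classification to be settled before lock, and says that in general no removals from analysis populations for deviations were planned. Section 4.5.3 would exclude only for a major deviation that confounds efficacy. Nothing here shows that a haemoglobin below 9 g/dL would do so.

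**Conclusion.** The limit is wrong as written, in both places, by a factor of 10 if 9 g/dL was meant. That intention is an inference, though a very safe one. The fault is confined to this one line and is one of eligibility wording. The documents do not show that any site applied the literal limit or treated a subject on the strength of it. Severity is minor.

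**What to change.** After the sponsor confirms the intended unit, change 8a to at least 9 g/dL (90 g/L) in the synopsis and in Section 9.1. If this is done as a formal amendment, Protocol Section 17.6 also requires investigator signature, IRB/IEC approval and FDA notification. With 40 subjects already treated, the main value of the corrected text is an accurate record and a clean line for any later protocol.

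In the study report, add a short statement that the unit was corrected, and say whether any treated subject had a pre-treatment haemoglobin below 9 g/dL. The source is the hematology listing planned in SAP Section 9.2.1. Give the unit explicitly, because SAP Section 9.2 reports laboratory data in the central laboratory's units without conversion. Make no new rule on deviations or per-protocol membership.

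The cost is one unit in two places and one descriptive statement. No reanalysis is needed.
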